#### 3.5. Statistical Analyses

**3.5.1.** Primary Analysis. Using SAS 9.4, primary analyses will be performed based on an intentto-treat basis. Two-sided significance levels of p<0.05 will be used for all analyses. Demographic (ethnicity, age, marital status) and other baseline variables (e.g., severity and chronicity) will be compared for potential differences between study groups using descriptive statistics (means, standard deviations, proportions) and the associated statistical tests (t-tests, chi-square tests). Those who drop out of the study will also be compared to those completing the study on baseline indices including maternal education and occupation. The primary outcome of noninferiority in EPDS scores will be compared between groups (telemedicine vs in-person, and specialist vs NSP) at 3-months using a t-test. The assessment period will be extended in the event that there is a hiatus to treatment due to significant perinatal-related life events (e.g., giving birth, obstetrical complications or COVID-19). One t-test will be run to assess this and compare modes (is telemedicine non-inferior to in-person). Another t-test will be run to assess this and compare agents (is non-specialist non-inferior to specialist). Each t-test will look at the confidence interval around the difference in EPDS scores (say between telemedicine and inperson), and see if the upper bound contains the 10% (provider) or 13% (modality) noninferiority margin (upper bound for the case in which we take the difference to be telemedicine minus in-person). We will conduct a sensitivity analysis to examine potential differences in baseline and outcome depressive symptoms and anxiety symptom scores to determine whether participants who were recruited and received treatment during the COVID-19 outbreak differed significantly from the larger sample.

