In addition, we will run a linear regression model with mode, agent and a mode by agent interaction term to assess whether an interaction between mode and agent exists. In the unlikely event that randomization was not able to reduce bias by balancing out confounders, we will assess for confounding. This will be carried out by assessing each potential confounder individually in relation to the key predictor (mode or agent) and seeing if the potential confounder impacts the parameter estimate of the key predictor using the 10% change in estimate approach. The potential confounder would also need to be significantly related to the EPDS score outcome. Should any confounders exist, they'll will be included in all of the previously mentioned analyses. Rules on the number of variables allowed in a multivariable model will be followed. The rule on number of variables in a linear regression is to take the total number of observations divided by 10. Given our trial sample size, we will not have any concerns with overfitting our linear model for our covariates of interest (education level, marital status, ethnicity, baseline severity and chronicity, timing of treatment, compliance, perceived support and medication).

Our study statistician and two independent methodological consultants have reviewed and approved this plan of analysis.

**3.5.2. Secondary Analysis.** In our secondary analysis, we are interested in: i) assessing the trend in EPDS scores over time (baseline, 3, 6- and 12-months post-randomization) between

groups (telemedicine vs in-person, and specialist vs NSP). This will involve the use of linear mixed models adjusting for possible covariates including baseline depression symptoms, medication, treatment dosage, and child age when assessing child outcomes. Mothers will be taken as a random effect and the models will include a treatment- by- time interaction term; ii) the same set of analyses will be conducted for anxiety symptoms (GAD-7). All child outcomes, including child mental development and the provision of psychosocial stimulation by the mother, will be compared between two groups (antenatal vs. postnatal) at 6-24 months post-childbirth using a two-sample two-sided t-test. Sensitivity analyses will be carried out excluding those who dropped out after first session to see if the results are comparable to the entire study group. No interim analyses will be carried out.

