1.6.2. Primary Aim 2 (Telemedicine vs. In-Person) Comparison

The primary outcome measure is an EPDS mean score at 3 months post-randomization. The sample size calculation is based on an EPDS mean estimate of 7.93 (SD=4.68)³⁰. Using a non-inferiority margin of 13% (i.e., EPDS score of 1.03 in relation to the mean), and an alpha=0.05, we require an additional 268 IP participants ([Table 4](#)).

Table 4: Non-inferiority margin in relation to sample size for Phase 3 comparisons

Non-inferiority margin	Power	Sample size per primary question	Total sample size + 10% dropout*	Total sample size + 20% dropout
10%	80%	431	958	1078
13%	80%	241	536 (268 per group)	604
14%	80%	221	492 (246 per group)	556

*Current dropout rates are <10% at primary outcome of 3-months post-randomization

When combined with the 958 TM participants, this yields a total study sample size of N=1,226 which accounts for 10% loss to follow-up ([Table 5](#)).

Table 5: Primary aims and required sample sizes

Primary Aim [¥]	Non-inferiority Margin	Power	Required sample size + 10% drop out
SP vs. NSP [¥]	10%	88%	958 telemedicine
IP vs. Telemedicine	13%	80%	268 in-person*
	Total		N=1226*

[¥]We acknowledge that the in-person sample is contained in the first hypothesis. This will result in the SP vs NSP comparison having up to 88% power. *We will over-recruit to account for protocol deviations where participants were switched from in-person to telemedicine due to the COVID-19 pandemic.

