3.4. Outcome analysis

3.4.1. Primary Analysis

All analyses will be run as both intent-to-treat (ITT, i.e., group that the participant was randomized to) and per protocol (i.e., group participant actually participated in*). SAS Version 9.4³⁵ or later will be used for all analyses. For non-inferiority analyses, a successful result will be based on the upper bound of the 95% confidence interval being less than or equal to the non-inferiority margin. Based on recent guidelines^{28, 29}, we will not adjust our two primary hypotheses for multiplicity as they do not involve different endpoints (i.e. both hypotheses test EPDS scores). For secondary superiority hypotheses, a two-sided significance level of $p<0.05$ will be used to denote statistical significance. Descriptive statistics will be calculated for all variables of interest. Continuous measures such as age and depressive symptoms will be summarized using means and standard deviations, whereas categorical measures will be summarized using counts and percentages.

*Note: The trial has n=21 protocol deviations. This number has been consistent since the last major COVID wave (March 2022).

Demographic (e.g., ethnicity, age, marital status) and other baseline variables (e.g., severity and chronicity) will be compared for potential differences between study groups (TM vs IP, and SP vs NSP) using two sample two sided t-tests for continuous variables (or Wilcoxon rank sum test in the case of non-normal data), and chi-square analyses for categorical variables (Fisher's exact tests in the case of low expected cell sizes). Those who withdrew from the trial will be compared to those who continued on baseline indices including maternal education and occupation.

The primary outcome of non-inferiority in EPDS scores will be compared between NSP vs. SP and TM vs. IP groups at 3-months using a t-test with a 10% and 13% margins of non-inferiority, respectively.

Primary Aim 1: Examine if a brief, BA psychological treatment delivered by non-specialist providers (NSP) is as effective in treating perinatal depressive symptoms as specialist-delivered treatment.

Aim 1 is to show that NSP is non-inferior to SP (N=479 per group, SPs vs NSPs, [Table 3](#)).

Primary Aim 2: Examine if a brief BA psychological treatment delivered through telemedicine (TM) is as effective in treating perinatal depressive symptoms as in-person treatment (IP).

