Aim 2 is to show that TM is non-inferior to in-person (N=268 per group, IP vs TM, [Table 4](#)).

Aim 1 and Aim 2 will initially be analyzed using a non-inferiority t-test (under the assumption that randomization will serve to balance out potential confounders). Each t-test will look at the confidence interval around the difference in EPDS scores (say between TM and IP) and see if the upper bound contains the non-inferiority margin (upper bound for the case in which we take the difference to be TM minus IP). In addition, we will run a linear regression model with mode, agent, and a mode by agent interaction term to assess whether an interaction between mode and agent exists. In the unlikely event that randomization was not able to reduce bias by balancing out confounders, we will adjust for variables found to be imbalanced at baseline.

Rules on the number of variables allowed in a multivariable model will be followed. The rule on number of variables in a **linear** regression is to take the total number of observations divided by 10. Given our trial sample size, we do not have any concerns with overfitting our linear model for our **covariates of interest** (education level, marital status, ethnicity, baseline severity and chronicity, timing of treatment, compliance, perceived support, and medication). For the **logistic** regression analyses, the number of predictors will be based on the smaller of the two outcome categories divided by 10^{36} .

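### The primary t-test omits entry EPDS and the randomisation strata, and two differently worded conditional adjustment rules leave it unsettled which confidence interval decides non-inferiority

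*SAP*

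**What the plan says.** **Deciding test.** SAP 3.4.1 compares EPDS between NSP and SP and between TM and IP "at 3-months using a t-test with a 10% and 13% margins of non-inferiority, respectively", and adds that "Aim 1 and Aim 2 will initially be analyzed using a non-inferiority t-test". Protocol 3.5.1 likewise runs two t-tests and will "see if the upper bound contains the 10% (provider) or 13% (modality) noninferiority margin". The additional regression in both documents holds only mode, agent and their interaction.

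**Strata and entry score.** Randomisation is stratified by perinatal period within site (Protocol 2.8, SAP 1.5). EPDS is required at screening because it sets eligibility (Protocol 2.7.1). SAP 1.2 calls site a potential covariate, and SAP 3.1 promises adjustment for site correlations when Toronto patients are referred between sites. Neither statement puts site in the primary model.

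**Conditional adjustment.** The SAP says that if randomisation does not balance confounders, "we will adjust for variables found to be imbalanced at baseline"; baseline groups are compared "using two sample two sided t-tests for continuous variables" and chi-square tests for categorical ones. The Protocol says: "In the unlikely event that randomization was not able to reduce bias by balancing out confounders, we will assess for confounding". It then applies a 10% change-in-estimate criterion plus a significant association with EPDS, and puts any confounder found into all the analyses described before it.

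**Candidate covariates.** The SAP list includes "baseline severity and chronicity, timing of treatment, compliance, perceived support, and medication"; the Protocol list is the same. Protocol 2.2.2 defines compliance by the number of sessions attended. Protocol 3.5.2 names treatment dosage as a possible covariate in the secondary mixed models.

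**The concern.** Three matters are involved.

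1. **Precision.** A variable related to 3-month EPDS and known before randomisation narrows the interval that is compared with the margin. Leaving out entry EPDS and the strata gives that up, although the sponsor itself lists baseline severity and timing of treatment as covariates of interest.
2. **Pre-specification.** The two rules use different criteria. The SAP calls the t-test the initial analysis, and the Protocol carries selected covariates back into the earlier analyses, which include the t-tests. A t-test cannot hold covariates, so a second result would then exist, and no sentence says which one is set against 0.79 or 1.03.
3. **Compliance.** Attendance follows randomisation and may be affected by provider or mode. The required number of sessions also falls when session EPDS scores are below 10 (Protocol 2.2.2), so compliance partly reflects EPDS during treatment. If a less effective arm works less well partly because fewer women attend, adjusting for attendance removes that part of the deficit and favours a finding of non-inferiority.

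**Working it through.** **Inputs.** SD 4.68, Aim 1 margin 0.793 and true difference 0 (SAP Table 3); N = 1,226 with 10% loss (SAP 1.6.2); success when the upper bound of the 95% CI is at or below the margin (SAP 3.4.1). Assumed: the correlation r between entry and 3-month EPDS. The documents give no r, and it may be low because entry requires EPDS of at least 10, which restricts the range.

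**Step 1: the plan's own figures.** SE = SD × √(2/n). With n = 431 per group, SE = 4.68 × √(2/431) = 0.319, and noncentral-t power at one-sided 0.05 is 0.800, as in Table 3. With n = 1,226 × 0.9 / 2, about 551 per group, power at one-sided 0.05 is 0.878. This reproduces the SAP footnote: "This will result in the SP vs NSP comparison having up to 88% power".

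**Step 2: adding entry EPDS.** The residual SD becomes 4.68 × √(1 − r²). With 551 per group:

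| r | Residual SD | SE | 95% CI half-width | Power, one-sided 0.025 | Power, one-sided 0.05 |
|---|---|---|---|---|---|
| 0 (t-test) | 4.68 | 0.282 | 0.55 | 80% | 88% |
| 0.2 | 4.59 | 0.276 | 0.54 | 82% | 89% |
| 0.3 | 4.46 | 0.269 | 0.53 | 84% | 90% |
| 0.5 | 4.05 | 0.244 | 0.48 | 90% | 95% |

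One-sided 0.025 corresponds to a two-sided 95% CI; one-sided 0.05 is the level that reproduces the sample size.

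**Step 3: how the two rules act on entry EPDS.** Adjustment moves the estimate by a chance amount with SD of about r × SE. At r = 0.3 this is 0.3 × 0.282 = 0.085. If the true difference is 0, an estimate one SE from zero is 0.282, and 10% of it is 0.028. The Protocol criterion is therefore easily met once it is applied. In 20,000 simulated Aim 1 trials (true difference 0; r = 0.2, 0.3, 0.5):

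| Rule | Entry EPDS selected | Verdict differs from t-test |
|---|---|---|
| SAP, imbalance read as p<0.05 | about 5% | 0.8%, 1.0%, 1.6% |
| Protocol criterion, gate ignored | 71%, 80%, 89% | 4.2%, 6.3%, 11.1% |
| Protocol criterion, gate read as p<0.05 imbalance in entry EPDS | – | 0.8%, 1.0%, 1.6% |
| Model with entry EPDS always fitted | 100% | 4.7%, 6.9%, 12.2% |

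**Step 4: false non-inferiority.** With a true deficit equal to the margin (0.793), the t-test, the always-adjusted model, the SAP rule and the Protocol rule each declare non-inferiority in about 2.5% of trials (2.3% to 2.7%). Taking whichever result is most favourable gives 2.8% to 3.7%.

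**Step 5: compliance.** The part of a deficit removed by adjustment is roughly the compliance gap times the EPDS difference associated with compliance. Neither is in the documents. As illustration only, gaps of 5 to 15 percentage points and differences of 2 to 4 EPDS points give 0.05 × 2 = 0.1 to 0.15 × 4 = 0.6 points, against a margin of 0.79.

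**The case against.** The strongest reply is that little harm follows. The Aim 1 t-test is valid, the precision gain depends wholly on an unknown r, and at the plan's own alpha the unadjusted power is already 88%. Both documents attach the margins to the t-test, so the deciding result is fairly clear. Protocol 3.5.1 sets two-sided p<0.05 for all analyses just before it describes the baseline comparisons, which gives imbalance a natural threshold. Compliance appears only in the sentence about overfitting, and treatment dosage only in secondary models.

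Much of this stands. Two stronger readings are tempting, and the documents do not support them.

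- **That the conflicting rules inflate false claims.** A reader might infer this from the 4% to 11% of verdicts that change under the Protocol criterion. The recommended model differs from the t-test just as often (5% to 12%), so the figure only measures how far adjusted and unadjusted analyses disagree. Step 4 shows no material inflation. The contrast between the rules also disappears if the Protocol's opening condition means p<0.05 imbalance in entry EPDS itself.
- **That adjusting for compliance would raise the false non-inferiority rate by a stated amount.** This needs the Protocol route to be opened, compliance to be treated as a confounder, a true deficit at the margin, a compliance gap and a mediated share. The documents supply none of these figures.

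What the reply does not remove: the variables are collected and unused in the primary model, the two rules are worded differently, the Protocol's carry-back clause leaves the deciding interval open, and a post-randomisation variable is on both lists.

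**Conclusion.** The point holds as a loss of precision and of pre-specification, and it should be fixed. For Aim 1 with two-sided 95% CIs, entry EPDS raises power from 80% to between 82% and 90% for r from 0.2 to 0.5; at one-sided 0.05 the move is from 88% to between 89% and 95%. These gains rest on the assumed r, and a low value is plausible. For baseline covariates, type I error is not materially affected.

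Compliance is a separate fault of direction. The SAP rule cannot select it, because compliance does not exist at baseline. The Protocol rule could if invoked, and the bias would then tend to favour non-inferiority. Its size is unknown from the documents.

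**What to change.** In SAP 3.4.1 and Protocol 3.5.1:

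- State that one pre-specified linear model decides both aims: 3-month EPDS on agent, mode, entry EPDS, perinatal period and site, with the margins of 0.79 (agent) and 1.03 (mode) applied to its 95% CIs. Keep the unadjusted t-test as a sensitivity analysis.
- Delete the SAP imbalance rule and the Protocol change-in-estimate rule.
- Remove compliance from both covariate lists, and treatment dosage from the treatment-effect models in Protocol 3.5.2.
- Define entry EPDS as the screening score, including the recent chart scores that Protocol 2.7.1 permits, because it is required of every participant. Protocol Table 6, SAP Table 2 and SAP 3.4.2.2 refer to a baseline EPDS, whereas SAP Appendix 1 ticks screening and not baseline; reconcile these.

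The cost is wording only. All variables are collected and the sample size is unchanged. This model does not resolve the changing TM:IP allocation ratio (SAP 1.5) for Aim 2, which is a separate decision.

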3.4.1.1. COVID-related Adjustments (Phase Analysis)

In order to determine whether the participants recruited in Phase 2 can be combined with those in Phase 3 in the larger trial, we will examine a potential interaction between group (SP, NSP) and phase (2 and 3) in relation to change in EPDS and GAD scores. To examine this, a linear mixed model will be run for the outcome EPDS and another for the outcome GAD. Each model will contain a group (SP, NSP), Phase (2 and 3), and a group by phase interaction term. A comparison of Phase 1 (pre COVID phase) to Phase 3 (return to IP phase) will not be carried out as the sample size in the first phase (n=23) is too small to detect statistical differences; however, we will conduct a sensitivity analysis on our primary outcome (EPDS scores at 3-month post-randomization) which includes this portion of the sample.

The study analyses will be carried out as originally planned on the entire sample of participants across all 3 phases. Should we find a group by phase interaction, we will also run separate analyses by phase (2 and 3) and compare their results to the model on the entire sample.

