1.5. Randomization

All SUMMIT participants are stratified by perinatal period (antenatal vs. postnatal) and were initially (Phase 1) randomized within site to one of four arms (see [Figure 2](#)). However, during the early part of the COVID-19 pandemic (Phase 2) when in-person care was prohibited, participants were randomized to only one of two arms: TM NSP and TM SP ([Figure 2](#)). All sites resumed randomization to all 4 arms 16 months later (Phase 3). Given that Phase 2 consisted of

Figure 2. Randomization strategy

*Randomization can shift to the two telemedicine arms based on site specific, COVID-related institutional restrictions, and once enrollment to in-person arms is complete.

randomizing participants exclusively to TM, there was an imbalance in participant assignment between the IP and TM arms. To address this, a weighted randomization approach (3:1, favoring IP) was used in Phase 3 in which a reduced percentage of

participants were randomized to the TM arms to ensure that the study's sample size targets will be met, and the final sample has an equal number of IP and TM participants. Due to the Omicron wave in December 2021 and January 2022, participants were randomized to TM-only again and randomization switched back to a 1:1 ratio. However, sites were permitted to switch between a 1:1 TM-only (2 arm) and a 1:1:1:1 both TM and IP (4 arm) randomization scheme based on site-specific COVID restrictions and Infection Prevention and Control (IPAC) recommendations. Sites began resuming Phase 1 randomization to IP in the 1:1:1:1 ratio in January 2022, and all sites returned to Phase 1 randomization by April 2022. Randomization to all 4 arms will be followed until in-person arms are fully enrolled after which randomization 1:1 to the two telemedicine arms will be followed.

Table 2: SUMMIT Outcomes (A more detailed list can be found in [Appendix 1](#)).

Study Variable	Instrument	Outcome (Range)
Maternal: Measured at Baseline and 3*-, 6*- and 12*-months post-randomization		
Maternal Characteristics**	Trial Baseline Questionnaire ^{6,7}	Self-reported age, education level, gender identity and sexual orientation, marital status, immigrant status and ethnicity, clinical history with depression or anxiety (severity, chronicity, number of prior episodes, and age at first episode), occupational status, number of children, pregnancy intention, pregnancy history, delivery and birth.

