
COVID-related Analyses:
 
The starting models to address COVID-related Aim 1 will compare mean baseline EPDS scores and mean GAD scores between the time periods (Phase 2 vs. Phase 3). The model to address COVID-related Aim 2 will include potential moderators. Using our originally-stated mean on the EPDS=7.93 (SD=4.68)³⁰, our power calculation indicates that a sample size of n=87 in each time period (N=174 across the entire period; or 184 including a 5% drop-out rate) is required to detect a clinically-meaningful difference of two or more points on the EPDS. This sample size will be used for the same number of participants enrolled during Phase 2 and Phase 3 of the trial (addressing Aim 1). To address COVID-related Aim 2, assuming a correlation of 0.1 between covariates, the sample size will be inflated to 204 (102 per time period).
 
To address COVID-related Aim 3, qualitative analyses using the same methods discussed in section 3.4.7 will be performed. Qualitative data will be analyzed to identify key themes related to barriers and facilitators using content analysis. Both barriers and facilitators will be categorized into internal, interpersonal and structural themes related to intervention delivery, impact and motivation, content and training and supervision.
	
COVID-related aim 1: Examining whether perinatal participants experience higher levels of depressive and anxiety symptoms during Phase 2 compared to those in Phase 3, whereby; 'Phase 2' is defined as period when IP allocation is treated as TM and 'Phase 3' is defined as the period when participants are randomized to IP and TM allocations by weighted randomization approach.
 
COVID-related aim 2: Examining potential moderators (e.g., treatment preference, trauma symptoms) of COVID-19 on treatment response among perinatal participants.
 
COVID-related aim 3: Exploring barriers and facilitators related to resuming IP treatment sessions from a multi-stakeholder perspective.

References

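### The group-by-phase check in SAP 3.4.1.1 has no mode × agent term, so it cannot separate a COVID-phase effect on the SP/NSP comparison from an in-person effect

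*SAP*

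**What the plan says.** SAP 3.4.1.1 sets the question of whether women recruited in Phase 2 can be combined with those in Phase 3. To answer it, "we will examine a potential interaction between group (SP, NSP) and phase (2 and 3) in relation to change in EPDS and GAD scores". On the model, "a linear mixed model will be run for the outcome EPDS and another for the outcome GAD", and on its terms, "Each model will contain a group (SP, NSP), Phase (2 and 3), and a group by phase interaction term". The section names no mode term, no mode × agent term, no time term and no visit schedule. It then states that the main analyses use everyone from every phase, and that an interaction would only add separate Phase 2 and Phase 3 analyses for comparison.

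SAP 1.5 (Randomization) shows how closely phase follows mode. In Phase 2, "participants were randomized to only one of two arms: TM NSP and TM SP". Afterwards, "a weighted randomization approach (3:1, favoring IP) was used in Phase 3". After the Omicron interruption, "Sites began resuming Phase 1 randomization to IP in the 1:1:1:1 ratio in January 2022", and once the in-person arms were full, allocation was to be telemedicine only. SAP 3.4.1.1 does not say whether women from these later periods count as Phase 3. In SAP 3.4.9, Phase 3 "is defined as the period when participants are randomized to IP and TM allocations by weighted randomization approach".

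SAP 3.4.1 treats a mode × agent interaction as possible: "we will run a linear regression model with mode, agent, and a mode by agent interaction term". That regression has no phase term.

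**The concern.** Phase 2 has no in-person women and Phase 3 has many. If the NSP–SP difference is not the same in person as by telemedicine, the average NSP–SP difference will change between the phases even if the pandemic had no effect on it. The listed model attributes that change to phase. The opposite can also happen: a real phase effect can be cancelled by a mode × agent effect of the other sign.

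The regression in SAP 3.4.1 has the mirror problem. Its telemedicine women are a mix of Phases 2 and 3, while its in-person women come almost entirely from after Phase 2. Its mode × agent term can therefore absorb an agent × phase effect. Neither model separates the two explanations.

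At stake is how the check is read. A positive result would trigger by-phase analyses and might be reported as a COVID effect. A null result might be reported as evidence that the telemedicine-only cohort can be combined with the rest. As specified, the test supports neither statement.

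**Working it through.** **The plan's own figures.** The phase model has no stated sample size, power or alpha, so it has no figure of its own to reproduce. The neighbouring figures do reproduce. Margin 0.793, SD 4.68, one-sided alpha 0.05 and 80% power give 431 per group (SAP 1.6.1). A 2-point difference with SD 4.68 gives 86 per period by the normal approximation and 87 by the t distribution, assuming 80% power and two-sided 0.05. Then 174/0.95 gives 184 (SAP 3.4.9).

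**Expected coefficient.** Take a 3-month outcome and write the provider effect as NSP minus SP:
- δ is the effect by telemedicine in Phase 2;
- γ is the true change in that effect from Phase 2 to Phase 3;
- θ is the effect in person minus the effect by telemedicine (mode × agent);
- p is the in-person share in Phase 3, equal in both provider groups by randomisation.

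The Phase 2 effect is δ. The Phase 3 effect is δ + γ + pθ. The group × phase coefficient as written is therefore γ + pθ. With no COVID effect (γ = 0) it is pθ.

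**Numbers.** The documents give no value for θ. As a scale I use the two margins, 0.793 and 1.03 (SAP 1.6.1 and 1.6.2). The share p is 0.75 under 3:1 weighting and 0.50 under 1:1:1:1; 0.25 is added as a lower case.

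| p | θ = 0.793 | θ = 1.03 |
|---|---|---|
| 0.75 | 0.60 | 0.77 |
| 0.50 | 0.40 | 0.52 |
| 0.25 | 0.20 | 0.26 |

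**Simulation check.** With 400,000 women per phase, SD 4.68, p = 0.75, θ = 1.03 and γ = 0:
- model as written: 0.77 to 0.79;
- adding a mode main effect only: 0.77 to 0.79;
- adding mode and mode × agent, or using telemedicine women only: −0.05 to 0.02, which is zero within simulation error.

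With θ = 0 and a mode main effect of 1.03, group × phase is −0.04, again noise. Only the phase main effect moves, by about 0.79. With γ = −0.77 and θ = 1.03 the model as written returns 0.007, which is complete masking.

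**Time.** If EPDS from V visits including baseline is modelled without time, the coefficient is the baseline gap plus (V − 1)/V times the gap in change. That keeps 0.50 of the gap in change with two visits and 0.75 with four. The mode-driven term shrinks likewise, from 0.77 to 0.39 or 0.58. The table therefore applies to a 3-month outcome.

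**Precision after the fix.** The five terms plus the intercept make six parameters for six cells (Phase 2 telemedicine, Phase 3 telemedicine and Phase 3 in-person, each by SP and NSP). The model is saturated, so agent × phase is estimated from telemedicine women alone, with SE = 4.68 × √(4/n₂ + 4/n₃), where n₂ and n₃ are the telemedicine women in Phases 2 and 3. Phase sizes are not given. Assume constant accrual of 1,230/39 = 31.5 a month, 16 months of Phase 2 (505 women) and about 5 weighted months (158 women, of whom 39 telemedicine).
- Phase 3 as the weighted period only: SE = 4.68 × √(4/505 + 4/39) = 1.56, a 95% CI of about ±3.0. As written, with all 158 women, the SE is 0.85, or ±1.7.
- Phase 3 as everyone later, using the SAP Table 5 totals and half of the 23 Phase 1 women in each mode: telemedicine 958 − 505 − 11.5 ≈ 441 and in-person 268 − 11.5 ≈ 257, so p ≈ 0.37. SE = 4.68 × √(4/505 + 4/441) = 0.61, or ±1.2.

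These are orders of magnitude, before dropout and baseline adjustment. The counts in SAP 1.4 (30 women before one measure was added in April 2020, 170 before another in June 2020) show that accrual was not constant.

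**The case against.** - **Nothing primary depends on it.** This stands. A reader might infer from the section's opening that the test decides whether the phases are pooled. The same section pools them regardless.
- **Heterogeneity is heterogeneity.** Group × phase, as written, validly asks whether the SP/NSP difference varies between the cohorts as recruited, and that bears on pooling whatever the cause. This stands in part. But the section is headed as a COVID adjustment, and the model cannot attribute a difference to COVID. A null result may also reflect two effects cancelling.
- **The time term may simply be unlisted.** The section says change and specifies a mixed model, and the trajectory and severity models in SAP 3.4.2.2 and 3.4.2.3 name a time interaction. A reader might infer that the model does not test change at all. The documents support only that the specification is incomplete. Nor do they support a claim that averaging over visits leaves the information of only 25% to 35% of the sample. That figure needs two visits and correlations of 0.3 to 0.5. With four visits and an equal effect at each follow-up, 0.75² × (1 − ρ²) / ((1 + 3ρ)/4) gives 108%, 86% and 68% at ρ = 0.3, 0.4 and 0.5.
- **The repair costs precision.** This stands and should be stated with it.

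**Conclusion.** The concern holds in a limited form. As listed, the model estimates the phase effect on the SP/NSP comparison plus the Phase 3 in-person share times the mode × agent interaction. For an assumed interaction of 0.79 to 1.03 points on 3-month EPDS, the second part is about 0.6 to 0.8 at 75% in-person and 0.4 to 0.5 at 50%, in either direction. For comparison, the provider margin is 0.79. If the mode × agent interaction is zero, group × phase is not biased, but the plan itself does not take that for granted.

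A reader might infer that the fault is the missing mode main effect. It is not: provider type is randomised within each phase, so that omission moves only the phase main effect. A reader might also assume a larger interaction, for example 1.5 points, giving 0.75 × 1.5 = 1.1. The documents give no basis for any particular value. The 75% share is likewise not settled, because the extent of Phase 3 is not stated.

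The damage is to the poolability check and the trigger for by-phase analyses. The primary t-tests are unchanged. Since the correction needs no new data, it should be made.

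**What to change.** In SAP 3.4.1.1:

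1. Fit agent, mode, phase, agent × mode and agent × phase in one model, or run the phase check in telemedicine women only. Do not add a mode main effect alone.
2. Use 3-month EPDS, and separately GAD-7, adjusted for the screening score; SAP Appendix 1 records both scales at screening. If a repeated-measures model is preferred, name the visits, include time and group × phase × time, and either limit it to telemedicine women or add the matching mode terms. A three-way term fitted to everyone without mode terms is not equivalent.
3. State which randomisation periods count as Phase 3, including the later 1:1:1:1 and telemedicine-only periods.
4. Report the interaction with its 95% CI, and state that a non-significant result is not proof of poolability.

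The cost is a few sentences and no new data. The downside is precision: agent × phase is then informed only by telemedicine women, markedly so if Phase 3 means the weighted period alone (roughly ±3 points under the accrual assumed above, against ±1.2 if all later women count).
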